Sodium Bicarbonate to Prevent Acute Kidney Injury in Children Undergoing Cardiac Surgery: A Randomized Clinical Trial

Principal Investigator: [name] MD

Co-Investigators: [name] MD, EdM, [name] MD, [name] MD, [name] MD and [name] MD

PART A. Specific Aims

With over 1 million operations a year, cardiac surgery with cardiopulmonary bypass (CPB) appears to be the second most common major contributor to acute kidney injury (AKI) in developed countries (1). AKI is a common and serious postoperative complication of CPB in children (2, 3). The pathophysiology of AKI is complex and not yet completely understood. Multiple causes of AKI after CPB have been proposed and include ischemia/ reperfusion, generation of reactive oxygen species (ROS), hemolysis, and activation of inflammatory pathways (4,5) To date, no simple, safe and effective intervention to prevent cardiopulmonary bypass-associated acute kidney injury in a broad patient population has been found. Sodium bicarbonate has shown promise in animal and clinical studies in the prevention of AKI.

The proposed study will investigate the effect of sodium bicarbonate on the prevention of acute kidney injury in children undergoing cardiac surgery with cardio-pulmonary bypass. We hypothesize that the occurrence of acute kidney injury will be less in children treated with sodium bicarbonate in the perioperative period when compared to placebo. The specific aims of this proposal are as follows:

Specific Aims:

1. To institute a prospective, randomized, double-blinded, placebo-controlled trial in pediatric subjects undergoing cardiac surgery to determine the efficacy of sodium bicarbonate on prevention of acute kidney injury as measured by pRIFLE criteria.
2. To examine whether treatment with sodium bicarbonate modifies the duration of acute kidney injury, fluid balance, hospital length of stay, need for dialysis, and progression to kidney failure.
3. To determine the relevance of NGAL as a biomarker to predict development of acute kidney injury.

PART B. Significance, Background and Preliminary Studies

Acute Kidney Injury

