To ensure that the chosen dose of sodium bicarbonate adequately alkalinizes the urine, we will briefly halt enrollment to blindly review urine pHs of the first 10 randomized subjects. The research nurse will be blinded to the patients' enrollment arm and the information regarding the results of the urine pH will not be available to the investigators until this interim analysis to assure appropriate blinding during the treatment of each patient. Since we have blocked randomization in groups of 10, we expect that half of the subjects will receive treatment with Sodium Bicarbonate. Therefore, we expect half of the subjects to have urine pH close to 7. If we find that urine is not adequately alkalinized, we will halt the study and submit a modification to the IRB to alter the dose of sodium bicarbonate.

VI. Study Outcomes

Demographic and Clinical Data

The medical record will be abstracted for the following variables: age, gender, diagnosis, previous surgical history, race, left ventricular ejection fraction on baseline echo, and current medications. Surgical parameters of cardio-pulmonary bypass time, ischemic time, surgical procedure, surgical complexity score, lowest temperature, use of circulatory arrest, use of cerebral perfusion, renal NIRS (measure of oxygen saturation of the renal vessels), medications administered, pH range, urine pH, surgical time, post-bypass time, estimated blood loss, and blood products administered will be measured. Cumulative fluid balance (daily Ins and Outs), hospital and intensive care unit length of stay, need for and duration of dialysis and medical complications will be recorded.

Serum NGAL is a biomarker of early AKI that often increases before serum creatinine. Specifically for this research study, serum NGAL and creatinine level will be drawn at the time of surgery and at 2, 4, 12, 24, and 48 hours.

As per routine care, creatinine will then be measured daily. pRIFLE level will be calculated on the maximum creatinine attained.

| pRIFLE Criteria | | |
|------------------------|---|---|
| | GFR | Urine Output |
| Risk | decrease by 25% | 0.5 mL/kg/h for 8 hours |
| Injury | decrease by 50% | 0.5 mL/kg/h for 16hours |
| Failure | decrease by 75% or GFR <35 | 0.3 mL/kg/h for 24 hours or anuric for 12 hours |
| Loss | Persistent failure 4 weeks | |
| End stage | End-stage renal disease (persistent failure 3 mo) | |

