2. Student’s t-test or Wilcoxon Rank Sum test for non-normally distributed variables will be used to compare values of duration of acute kidney injury, fluid balance, hospital length of stay, need for dialysis, and progression to kidney failure between groups. Pearson correlation and linear regression will be used to examine the association between duration of acute kidney injury, fluid balance, hospital length of stay, need for dialysis, and progression to kidney failure and development of AKI. Regression analysis will be adjusted for sex, age and race. Variables may be log transformed to improve the fit of the models.
3. Pearson correlation and linear regression will be used to analyze the association of NGAL with development of AKI.

II. Sample Size Estimates

Sample size estimates were calculated for the primary outcome of proportion that develop AKI in each of the two groups. Sample sizes were considered based on various effect sizes. Assuming 50% risk of AKI from our previous work, a drop from 50% AKI to:

35% would need 170 per group

30% would need 93 per group

25% would need 66 per group

20% would need 44 per group

In the literature, studies have used reductions between 20-35%. We aimed for somewhere in between. The comparison of 66 subjects in the treatment group and 66 subjects in the control group provides 80% power ($\alpha = 0.05$) to detect a difference from 0.5 in the control group to 0.25 (that is a 50% reduction in AKI) in the treatment group. nQuery software was utilized to calculate sample size.

III. Limitations

The proposed study is limited by the small sample size and heterogenous population. Given these limitations, we believe the results of the proposed study will be able to be generalized to the pediatric cardiac surgery population.

PART F. PROTECTION OF HUMAN SUBJECTS

Risk to Subjects

a. Human Subjects Involvement and Characteristics

The proposed study will involve human subjects, in particular, children and adolescents aged ≤ 18 years of age. The purpose of the study is to examine cardiac surgery in a pediatric population, therefore, other age groups are excluded from this study. Other inclusion/exclusion criteria are listed elsewhere in the protocol. This vulnerable population will be protected. Assent will be obtained from the participants and participants may withdraw from the study at any time.

b. Potential Risks

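### Aim 2's only adjusted models relate the outcomes to AKI instead of treatment arm, and for AKI duration and progression to pRIFLE F the association is built into the definitions

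*Combined protocol and SAP*

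**What the plan says.** - **The question.** Part A, Specific Aim 2: "To examine whether treatment with sodium bicarbonate modifies the duration of acute kidney injury", followed by fluid balance, hospital stay, dialysis and kidney failure. This is a question about treatment.
- **The treatment comparison.** Part E.I, item 2: a t-test or Wilcoxon test "will be used to compare values of duration of acute kidney injury" and the other four outcomes between groups. The general paragraph of Part E.I adds intention to treat, and chi-square for proportions.
- **The regressions and their covariates.** The same item continues: "Pearson correlation and linear regression will be used to examine the association between duration of acute kidney injury" and the other outcomes on one side, and AKI on the other. The list closes, and the covariates follow, with "need for dialysis, and progression to kidney failure and development of AKI. Regression analysis will be adjusted for sex, age and race". Treatment arm is not named, and no other adjusted model is given for Aim 2.
- **Transformation.** "Variables may be log transformed to improve the fit of the models", with no limit on which variables.
- **Definitions.** Part D.I defines AKI for the primary outcome as meeting pRIFLE or a creatinine rise of 0.3 mg/dl, and lists progression to pRIFLE F as a secondary outcome. Part D.VI gives the pRIFLE table. How AKI duration is coded for a child without AKI is not stated.
- **Data available.** Part D.VI records "Surgical parameters of cardio-pulmonary bypass time, ischemic time, surgical procedure, surgical complexity score", among others.

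**The concern.** The adjusted part of Aim 2 answers a different question from the aim. Relating an outcome to AKI shows whether children with AKI did worse. It does not show whether bicarbonate changed anything.

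There are three consequences.

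1. For AKI duration and progression to F, the explanatory variable is part of the outcome's own definition. A significant coefficient there would say nothing about the drug, yet it would appear under a treatment aim.
2. For stay, fluid balance and dialysis, AKI is a non-randomised event that occurs after randomisation. Operative severity can plausibly drive both AKI and these outcomes. The models adjust only for sex, age and race, although surgical complexity and bypass time are collected.
3. The open permission to log-transform reaches outcomes that can be zero or negative, where a plain log is undefined.

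**Working it through.** **1. The plan's own sizing figure.** Part E.II: 50% against 25% AKI, 80% power, two-sided alpha 0.05.
- Uncorrected: n = [1.96·√(2·0.375·0.625) + 0.8416·√(0.25 + 0.1875)]² / 0.25² = 57.7, so 58 per group.
- With continuity correction: (57.7/4)·[1 + √(1 + 4/(57.7·0.25))]² = 65.4, so 66 per group.

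The plan's 66 per group (132 in all) is reproduced with the correction. The point does not depend on it; it sets the trial size used below.

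**2. Does stage F imply AKI?** Each F criterion in the Part D.VI table, checked against Risk:
- A GFR fall of 75% exceeds the 25% needed for Risk.
- GFR below 35: clearance below 90 is excluded at entry (Part D.III), so the fall is at least 1 − 35/90 = 61%, again above 25%.
- Urine output of 0.3 mL/kg/h for 24 h, or anuria for 12 h, includes 8 h at or below 0.5 mL/kg/h.

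So P(F | no AKI) = 0 by construction, and the association of F with AKI can only be positive.

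**3. AKI duration.** There are two possible codings:
- *Zero without AKI.* Every child without AKI has 0 and every child with AKI has more than 0, so the association is forced.
- *Defined only in AKI cases.* AKI is then constant in the data analysed, and its coefficient cannot be estimated.

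**4. Size for duration, zero coding.** Let p be the AKI proportion and cv the coefficient of variation of duration among AKI cases. Then

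r = √[(1 − p)/(1 − p + cv²)].

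I assume exponential durations (cv = 1). Part D.V.c says 75% of patients have AKI lasting under 48 h, which gives a mean of 2/ln 4 = 1.44 days. The mean cancels in r.
- No treatment effect, p = 0.50: r = √(0.5/1.5) = 0.58, t = 0.577·√(130/0.667) = 8.1, against a critical value of 1.98.
- Planning rates, p = (0.50 + 0.25)/2 = 0.375: r = √(0.625/1.625) = 0.62.
- Much more variable durations, cv = 2, p = 0.50: r = √(0.5/4.5) = 0.33, t = 4.0.

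Simulation with exponential durations and 132 children (2,000 trials; models adjusted for age, sex and race):

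| Analysis of AKI duration | No effect (50% v 50%) | Planning rates (50% v 25%) |
|---|---|---|
| Regression on AKI, significant | 100% | 100% |
| Regression on treatment arm, significant | 5.1% | 48% |
| Wilcoxon by arm, significant | 5.2% | 83% |

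The median r for duration against AKI is about 0.59 with no effect. The AKI model gives the same answer whether or not the drug works. The two treatment comparisons distinguish the cases.

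**5. Size for F.** With 66 children with AKI, 66 without, and k reaching F, r = √[k/(132 − k)]. The 5% critical value is 0.171.
- k = 3: r = 0.15, not significant.
- k = 6: r = 0.22, significant.
- k = 10: r = 0.29, significant.

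The documents give no share of AKI reaching F. Simulated with no treatment effect:

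| Assumed share of AKI reaching F | Trials with F v AKI significant |
|---|---|
| 2% | about 3% |
| 5% | about 36% |
| 10% | about 87% |
| 15% | about 99% |

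Rates move by a few points between simulation runs and with adjustment. The direction is always positive; significance depends on the number of F cases.

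**6. Log transform.** With zero coding and a plain log, every child without AKI drops out. At planning rates that is 1 − 0.50 = 50% of controls and 1 − 0.25 = 75% of treated children, which is selection on the primary outcome. An offset would avoid this, but the plan names none.

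**The case against.** **Aim 2 is already answered.** The sentence before the regressions compares all five outcomes between randomised groups, and randomisation makes the unadjusted comparison valid. This stands. A reader might infer that the plan never tests the effect of bicarbonate on these outcomes, and the documents do not support that. Adjustment is optional here. The defect is that the adjustment offered is attached to another question.

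**The AKI models are a legitimate supplement.** Part B presents AKI as a risk factor for longer stay, so relating AKI to stay is a coherent secondary question. The plan calls it an association and nowhere says it would be read as evidence for the drug. This stands for stay, fluid balance and dialysis, though not with the present covariates. It does not rescue duration or F.

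**The roles of the variables are inferred.** The plan does not say which variable is dependent. AKI as explanatory is the natural reading. If AKI were the dependent variable, treatment would still be absent and the definitional link would remain.

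**Both uninformative regressions are bound to be significant.** A reader might infer this, but it goes too far. Significance is practically certain for duration only, and only with zero coding. For F it depends on a share that the documents do not give.

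**The log transform is permissive.** It is optional and may suit length of stay. The loss of children is conditional on zero coding and a plain log.

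**Conclusion.** The point holds as a recommended change to secondary analyses. It does not threaten the primary analysis or the unadjusted Aim 2 tests.

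- That treatment arm is absent from the only adjusted Aim 2 models follows from the text and needs no assumption.
- For F, the forced direction follows from the protocol's own definitions. The size does not: about 36% to 99% of null trials significant as the assumed share of AKI reaching F goes from 5% to 15%.
- For AKI duration, the model is either forced or cannot be fitted. The 100% rejection rate and r of about 0.59 assume zero coding, 50% AKI and exponential durations. The conclusion survives doubling the variability of duration (expected r 0.33, t about 4).
- For stay, fluid balance and dialysis, the AKI association is observational and weakly adjusted. The documents give no figures from which to size the confounding.

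**What to change.** In Part E.I, item 2:

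1. Keep the between-group tests.
2. Add a model for each Aim 2 outcome with treatment arm as the explanatory variable, adjusted for prespecified baseline covariates. Report each treatment effect with a 95% CI. Use logistic or exact methods for dialysis and stage F.
3. Delete the regressions of AKI duration and progression to F on AKI. State how AKI duration is coded in children without AKI.
4. Keep the AKI association for stay, fluid balance and dialysis only, labelled exploratory and observational. Add surgical complexity score, bypass time and treatment arm to its covariates.
5. Do not apply a plain log transform to outcomes that can be zero or negative.

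The cost is a few extra models and a few lines of text. Complexity score and bypass time are already recorded, so no new data are needed.

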Treatment Arm: At the start of the surgery, the patient will receive NaHCO₃ as a continuous infusion of D5% 1/3NS + 100 meq/L NaHCO₃ + 20 meq/L KCl at maintenance IVF (solution contains ~154 meq of sodium which is equivalent to normal saline). The NaHCO₃ infusion will continue for the first 24 hours after the discontinuation of CPB. After 24 hours of receiving the NaHCO₃ infusion, the IVF administered to the patient will be the standard solutions used in the PICU at CCMC.

Control Arm: At the start of surgery, patients in the control arm will receive D5% Normal Saline + 20 meq/L KCl at maintenance IVF. After 24 hours, standard IVF, not containing NaHCO₃ or Na acetate will be administered for the duration of the PICU stay as required, determined by the clinicians primarily caring for the patient postoperatively.

Primary Outcome Measure: The efficacy of sodium bicarbonate on prevention of AKI will be tested by comparing the proportion of subjects in each of the treatment arms who progress to AKI as measured by the Pediatric Risk, Failure, Loss of Function, and End-Stage Renal Disease (pRIFLE) criteria or an absolute increase in creatinine of 0.3mg/dl.

Secondary Outcome Measures:

1. Duration of acute kidney injury
2. Cumulative fluid balance
3. Hospital and intensive care unit length of stay
4. Need for dialysis
5. Progression to pRIFLE criteria F
6. Association of NGAL as a biomarker to predict development of acute kidney injury
7. Length of mechanical ventilation
8. Change in acid-base status

II. Study Sites

Subjects will be recruited from the Cardiothoracic Surgery Division of the Cohen Children's Medical Center of New York of North Shore-LIJ Health Systems (CCMC) in New Hyde Park, New York

III. Study Subjects

Patients from CCMC come from a large geographic area with a diverse racial composition. There are currently 150 children ≤ 18 years that undergo cardiac surgery with cardiopulmonary bypass per year at CCMC. Consecutive patients scheduled for cardiac surgery who meet eligibility criteria will be invited to participate in the study.

Eligibility criteria include:

Inclusion Criteria

- 1) Subjects age ≤ 18 years
- 2) Subjects scheduled for cardiac surgery with cardiopulmonary bypass

Exclusion Criteria

- 1) Subjects with abnormal creatinine clearance (< 90 ml/min/1.7m²) as measured by the Schwartz formula

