Treatment Arm: Patients randomized to the intervention of receiving NaHCO₃ perioperatively will initially receive the current standard anesthetic and perfusion approach at CCMC, which includes a cardiopulmonary pump priming solution containing 0.2mEq per milliliter of crystalloid. At the start of the surgery, the patient will begin to receive NaHCO₃ as a continuous infusion of D5% 1/3NS + 100 meq/L NaHCO₃ + 20 meq/L KCl at maintenance IVF (solution contains ~154 meq of sodium which is equivalent to normal saline). The strength of NaHCO₃ is based on a dose of 150 meq/m²/day (reference range 120-200mEq/m²/day [Lexicomp, 18th Ed., 2011-12]) and IVF maintenance of 1500 ml/m²/day. While the patient is undergoing CPB, calculated base deficits more negative than -3 will be corrected by giving NaHCO₃ according to the formula: base deficit * patient weight in kilograms/ 3. Tromethamine (THAM) may be used in the neonatal population while undergoing CPB if the serum sodium levels have increased to greater than 145 mEq/dL. Blood gas serum sodium, potassium and calcium will be monitored during the surgery and corrections will be made by the anesthesiologist. The NaHCO₃ infusion will continue for the first 24 hours after the discontinuation of CPB (based on current data from CCMC PICU: 85% of patients who develop AKI do so in the first 24 hours, and duration of AKI is <48 hours in 75% patients (reference Aydin, Annals of Thoracic Surgery, 2012). After 24 hours of receiving the NaHCO₃ infusion, the IVF administered to the patient will be the standard solutions used in the PICU at CCMC, notably a sodium concentration with dextrose along the spectrum of D5 0.33% NaCl through D5 0.45% NaCl, depending on the patient's serum electrolyte profile.

Control Arm: At the start of surgery, patients in the control arm will receive D5% Normal Saline + 20 meq/L KCL at maintenance IVF. The standard approach to perfusion for CPB, including the pump prime solution containing NaHCO₃ as well as replacement of NaHCO₃ for calculated base deficits will be administered as described above. After 24 hours, standard IVF, not containing NaHCO₃ or Na acetate will be administered for

the duration of the PICU stay as required, determined by the clinicians primarily caring for the patient postoperatively.

d. Hospital Course

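### Aim 3 concerns NGAL as a predictor of AKI, but the plan tests only association, names no NGAL draw, and does not require the draw to precede AKI

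*Combined protocol and SAP*

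**What the plan says.** - **Objective.** Part A, Specific Aim 3: "To determine the relevance of NGAL as a biomarker to predict development of acute kidney injury". Part D, I, secondary outcome 6: "Association of NGAL as a biomarker to predict development of acute kidney injury".
- **Method.** Part E, I, item 3, in full: "Pearson correlation and linear regression will be used to analyze the association of NGAL with development of AKI". The document mentions no ROC curve, AUC, sensitivity, specificity, cut-off or logistic model.
- **Sampling.** Part D, VI: "serum NGAL and creatinine level will be drawn at the time of surgery and at 2, 4, 12, 24, and 48 hours". No draw, peak or change from baseline is singled out as the predictor.
- **Rationale.** Part D, VI: "Serum NGAL is a biomarker of early AKI that often increases before serum creatinine".
- **Timing of AKI.** Part D, V.c, citing the centre's own data: "85% of patients who develop AKI do so in the first 24 hours".
- **Aim 2 (minor points).** Part E, I, item 2 puts two yes/no outcomes under the t-test or Wilcoxon test: "need for dialysis, and progression to kidney failure between groups". It then plans correlation and linear regression between the Aim 2 outcomes and AKI itself, a list that ends: "need for dialysis, and progression to kidney failure and development of AKI". The general text of Part E, I assigns proportions to chi-square.

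**The concern.** A predictor has to be measured before the event and judged by how well it sorts future cases from non-cases. The plan secures neither. A correlation coefficient is not a measure of discrimination, and its size also depends on how common AKI is. Since NGAL is valued here for rising ahead of creatinine, a sample taken after creatinine has already risen cannot test that property.

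One of the three specific aims could therefore end with a significant result that mainly reflects AKI already present at the draw, or that comes from the most favourable of six draws. A reader would not learn how useful an early NGAL value is.

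Two smaller points sit in Aim 2. AKI duration and progression to stage F are associated with AKI by construction. Need for dialysis and progression to F are proportions, but they are listed under tests for continuous data.

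**Working it through.** **Inputs.** 66 children per arm, AKI 50% against 25%, two-sided 0.05 (Part E, I and II); six NGAL draws (Part D, VI); 85% of AKI within 24 h (Part D, V.c). The plan gives no power or precision for Aim 3. Its only sample-size figure for this design, 66 per group, concerns the primary outcome. It is reproduced with a continuity correction (58 without).

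**1. What a significant correlation implies.** Expected cases: 66 × 0.50 + 66 × 0.25 = 49.5 of 132, so p = 0.375. The critical t on 130 df is 1.978.
- r = t/√(130 + t²) = 1.978/√(130 + 3.914) = 0.171; r² = 2.9%.
- d = r/√[(1 − r²)p(1 − p)] = 0.171/√(0.971 × 0.234) = 0.358.
- Equal-variance binormal AUC = Φ(d/√2) = Φ(0.253) = 0.60.
- Sensitivity at 80% specificity = 1 − Φ(0.842 − 0.358) = 31%.

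A just-significant result is therefore compatible with poor prediction.

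**2. Cases still to come at 24 h** (both clocks taken as post-operative).
- AKI 50%/25%: 49.5 × 0.15 = 7.4 (95% range 3 to 13).
- AKI 50% in both arms: 66 × 0.15 = 9.9 (4 to 16).

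**3. Illustration of a late draw.** Suppose the 24 h draw were the predictor. Assume that log NGAL is shifted only in the 85% of cases already present (AUC 0.70 to 0.90) and says nothing about later cases (AUC 0.50). The shift is d = √2·Φ⁻¹(AUC) = 0.742, 1.190 and 1.812 for AUC 0.70, 0.80 and 0.90. In 20,000 simulated trials per setting:

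| AKI by arm | AUC 0.70 | AUC 0.80 | AUC 0.90 |
|---|---|---|---|
| 50%/25%, Pearson significant | 92.8% | 99.9% | 100% |
| 50%/50%, Pearson significant | 93.9% | 100% | 100% |

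A rank test on the same data is significant in about 92% to 100% of trials. An AUC in all children would read 0.85 × 0.70 + 0.15 × 0.50 = 0.67, up to 0.85 × 0.90 + 0.15 × 0.50 = 0.84. Replacing Pearson with an AUC does not cure this; the timing and the at-risk set do.

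**4. No named draw.** If all six draws were tested at 0.05 without adjustment and NGAL were unrelated to AKI, at least one would be significant in 26.7%, 20.4% or 13.7% of trials, for an assumed correlation between draws of 0, 0.5 or 0.8. The independence formula gives 1 − 0.95⁶ = 26.5%.

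**5. Precision of the repair.** Hanley-McNeil: SE² = [A(1 − A) + (n₁ − 1)(Q₁ − A²) + (n₀ − 1)(Q₂ − A²)]/(n₁n₀), with Q₁ = A/(2 − A) and Q₂ = 2A²/(1 + A). At A = 0.80, Q₁ = 0.667 and Q₂ = 0.711. Half-width = 1.96 × SE:

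| Share of cases after the draw | 49.5 cases, 82.5 non-cases | 66 and 66 |
|---|---|---|
| 100% | 0.083 | 0.076 |
| 90% | 0.086 | 0.079 |
| 75% | 0.093 | 0.085 |
| 50% | 0.111 | 0.100 |
| 15% (24 h draw) | 0.196 | 0.172 |

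The shares for early draws are assumptions; the document gives none.

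**6. Why the AUC of NGAL itself.** At 50%/25%, arm alone has AUC 0.5 + (33/49.5 − 33/82.5)/2 = 0.633. A model containing arm would credit NGAL with discrimination that comes from treatment.

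**7. Minor point on sparse events.** At 4 against 0 of 66, chi-square gives p = 0.042, the t-test 0.043 and Fisher's exact test 0.119.

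**The case against.** The planned test is sound for what it tests. Pearson correlation with a 0/1 variable is the point-biserial correlation, equivalent to a pooled t-test, and outcome 6 itself contains the word association. A reader might infer that the method is invalid for a binary outcome. It is not; it stops short of the objective. This stands and limits the point to a missing measure of discrimination and missing timing rules.

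A reader might also take the 93% to 100% figure as an error rate of the plan or a fault of Pearson. The document does not support that. It nowhere says that the 24 h draw will be the predictor, draws at 2, 4 and 12 h are already scheduled, the AUC inputs are assumed, and a rank test behaves in the same way. Likewise, 14% to 27% holds only if all six draws are tested unadjusted, on which the plan is silent. Its upper end needs uncorrelated repeat values in the same child.

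It is also tempting to say that the comparison by arm makes the Aim 2 regressions superfluous. That goes too far. If AKI duration is analysed only in children with AKI, the arms are compared within a group defined after randomisation, about 33 against 16.5 cases at the design rates.

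Finally, on the test for dialysis and stage F, the t-test and chi-square agree almost exactly in the example. The conflict is one of wording, and only the exact test for few events would change a result.

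**Conclusion.** The concern holds in limited form. The Aim 3 analysis can show that NGAL and AKI are associated. It cannot show how well NGAL predicts AKI, and it leaves open which draw counts and whether that draw precedes the event. The firmest figures are the significance threshold (r = 0.171, AUC about 0.60, under a binormal model at 37.5% AKI) and the 7 to 10 cases left after 24 h, which carries the centre's historical 85% over to this trial. The late-draw and six-draw results illustrate what the open choices permit and do not forecast what the trial will do. The primary comparison and the sample size are untouched. This is an inexpensive improvement that is worth making. The two Aim 2 points are minor.

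**What to change.** Amend Part E, I, item 3 before NGAL values are linked to AKI status. Doing so before unblinding is not enough: Aim 3 pools the arms, so a draw could be chosen on its results without knowing any allocation.

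1. Name one early post-operative draw as the predictor. The choice (2 h, for example) is the investigators'.
2. Restrict to children who do not yet meet the trial's AKI definition at that draw. Report the AUC of NGAL itself, with 95% CI, for AKI arising afterwards.
3. Use one definition for both the at-risk set and the later outcome: creatinine-based pRIFLE or the 0.3 mg/dl rise. State whether the urine-output criteria count, and over what period later AKI is counted.
4. Give sensitivity and specificity at a cut-off stated in advance, or label a data-derived cut-off exploratory.
5. For the adjusted association, use logistic regression of AKI on log NGAL with arm as a covariate.
6. Treat the other early draws as secondary, and 24 h and 48 h as descriptive.

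Minor, in item 2: drop the association of AKI duration and stage F with development of AKI. Analyse need for dialysis and progression to F as proportions, with an exact test when expected counts fall below 5 (fewer than 10 events in total at 66 per arm).

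**Cost.** SAP wording and a little analysis. No new samples are needed, since creatinine is already drawn with NGAL. The at-risk set holds fewer cases, so the interval widens, to an extent that depends on how many cases are already present at the named draw.
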